### **8.3.8 Disease Under Study**

Symptoms of DUS are those which might be expected to occur as a direct result of dyslipidemia. Events which are unequivocally due to DUS should not be reported as AEs during the study unless they meet SAE criteria or lead to discontinuation of the IMP.

### **8.3.9 Reporting of SAEs**

All SAEs must be reported whether or not considered causally related to the IMP. All SAEs will be recorded in the eCRF.

If any SAE occurs during the study, investigators or other site personnel will inform the appropriate Sponsor representatives within one day, ie, immediately but **no later than 24 hours** of when he or she becomes aware of it.

The designated Sponsor representative will work with the investigator to ensure that all the necessary information is provided to the AstraZeneca Patient Safety data entry site **within one calendar day** of initial receipt for fatal and life-threatening events **and within 5 calendar days** of initial receipt for all other SAEs.

For fatal or life-threatening AEs where important or relevant information is missing, active follow-up will be undertaken immediately. Investigators or other site personnel will inform the Sponsor representative of any follow-up information on a previously reported SAE within one calendar day, ie, immediately but **no later than 24 hours** of when he or she becomes aware of it.

Once the investigators or other site personnel indicate an AE is serious in the Electronic Data Capture (EDC) system, an automated email alert is sent to the designated Sponsor representative.

If the EDC system is not available, then the investigator or other study site staff reports the SAE via secure method to the appropriate Sponsor representative.

When the EDC is temporarily not accessible, the Sponsor Study Representative should confirm that the investigator/site staff enters the SAE in the AstraZeneca EDC when access resumes.

For further guidance on the definition of an SAE, see [Appendix B](#).

The reference document for definition of expectedness/listedness is the IB for the AstraZeneca IMP.

In the European Union, the Sponsor will comply with safety reporting requirements and procedures as described in the European Clinical Trials Regulation (EU) No 536/2014. All suspected unexpected serious adverse reactions (SUSARs) to investigational medicinal product will be reported to the EudraVigilance database within the required regulatory timelines.

### **8.3.10      Pregnancy**

Participants will be instructed that if they or their partner becomes pregnant during the study this should be reported to the investigator. The investigator should also be notified of pregnancy occurring during the study but confirmed after completion of the study. In the event that a participant's partner is subsequently found to be pregnant after the participant is included in the study, then consent will be sought from the partner (via the participant's request that their partner contact the study site) and, if granted, any pregnancy will be followed, and the status of mother and/or child will be reported to the Sponsor after delivery.

#### **8.3.10.1    Maternal Exposure**

Females of childbearing potential are not allowed to be included in this study. Should a pregnancy still occur, the study intervention should be discontinued immediately, and the pregnancy reported to the Sponsor.

Pregnancy itself is not regarded as an AE unless there is a suspicion that the study intervention may have interfered with the effectiveness of a contraceptive medication. Congenital anomalies/birth defects and spontaneous miscarriages should be reported and handled as SAEs. Elective abortions without complications should not be handled as AEs. The outcome of all pregnancies (spontaneous miscarriage, elective termination, ectopic pregnancy, normal birth or congenital anomaly/birth defect) should be followed up and documented even if the participant was discontinued from the study.

If any pregnancy occurs during the study, then the investigator or other site personnel informs the appropriate Sponsor representative immediately but no later than **24 hours** after he or she becomes aware of it.

The designated Sponsor representative works with the investigator to ensure that all relevant information is provided to the AstraZeneca Patient Safety data entry site **within one or 5 calendar days** for pregnancies associated with SAEs (Section [8.3.9](#)) and **within 30 days** for all other pregnancies.

The same timelines apply when outcome information is available.

#### **8.3.10.2    Paternal Exposure**

Male participants should refrain from fathering a child or donating sperm during the study and for 3 months following the last follow-up visit.

Pregnancy of the participant's partners is not considered to be an AE. However, the outcome of all pregnancies (spontaneous miscarriage, elective termination, ectopic pregnancy, normal birth or congenital anomaly), occurring from the date of the first dose until 10 months after the last dose should, if possible, be followed up and documented in the Pregnancy Report Form.

Consent from the pregnant partner must be obtained before the Pregnancy Report Form is completed.

### **8.3.11 Medication Error, Drug Abuse, and Drug Misuse**

#### **8.3.11.1 Timelines**

If an event of medication error, drug abuse, or drug misuse occurs during the study, then the investigator or other site personnel informs the appropriate Sponsor representative within **one calendar day**, ie, immediately but **no later than 24 hours** of when they become aware of it.

The designated Sponsor representative works with the investigator to ensure that all relevant information is completed within **one** (initial fatal/life-threatening or follow-up fatal/life-threatening) **or 5** (other serious initial and follow-up) **calendar days** if there is an SAE associated with the event of medication error, drug abuse, or misuse (Section [8.3.9](#)) and **within 30 days** for all other events.

#### **8.3.11.2 Medication Error**

For the purposes of this clinical study a medication error is an **unintended** failure or mistake in the treatment process for an IMP that either causes harm to the participant or has the potential to cause harm to the participant.

The full definition and examples of medication error can be found in Appendix [B 4](#).

#### **8.3.11.3 Drug Abuse**

Drug abuse is the persistent or sporadic **intentional**, non-therapeutic excessive use of IMP for a perceived reward or desired non-therapeutic effect.

The full definition and examples of drug abuse can be found in Appendix [B 4](#).

#### **8.3.11.4 Drug Misuse**

Drug misuse is the **intentional** and inappropriate use (by a study participant) of IMP for medicinal purposes outside of the authorized product information, or for unauthorized IMPs, outside the intended use as specified in the protocol and includes deliberate administration of the product by the wrong route.

The full definition and examples of drug misuse can be found in Appendix [B 4](#).

### **8.3.12 Reporting of Overdose**

For this study, any dose of AZD0780 greater than the planned dose within the planned study period will be considered an overdose.

- An overdose with associated AEs is recorded as the AE diagnoses/symptoms on the relevant AE modules in the eCRF and on the Overdose eCRF module.
- An overdose without associated symptoms is only reported on the Overdose eCRF module.

If an overdose on an IMP occurs in the course of the study, the investigator or other site personnel inform the appropriate Sponsor representative immediately, but **no later than 24 hours** of when he or she becomes aware of it.

The designated Sponsor representative works with the investigator to ensure that all relevant information is provided to the AstraZeneca Patient Safety data entry site **within one or 5 calendar days** for overdoses associated with an SAE (Section 8.3.9) and **within 30 days** for all other overdoses.

Refer to Section 6.8 for definition and treatment of overdose.

## 8.4 Pharmacokinetics

### 8.4.1 Collection of Samples for Pharmacokinetics

Blood samples will be collected for measurement of plasma concentrations of AZD0780 as specified in the SoA (Section 1.2). On days where PK samples are to be collected the patient should refrain from taking the study medication prior to coming to the clinic. The PK samples are to be collected prior to administering the study medication at the clinic.

Plasma concentrations will be summarized by treatment (dose level of AZD0780) for each sampling time point, using descriptive statistics based on the PK analysis set and included in the CSR.

Samples will be collected, labeled, stored, and shipped as detailed in the Laboratory Manual.

PK data from this study, possibly together with data from other studies, may be used for population PK/PD analysis. The results of any such modeling activity will be provided in a separate report (as an appendix to the CSR or as a stand-alone report).

### 8.4.2 Determination of Drug Concentration

Samples for determination of drug concentration in plasma will be assayed by Labcorp Bioanalytical Services LLC on behalf of the Sponsor, using an appropriately validated bioanalytical method. Full details of the analytical method used will be described in a separate Bioanalytical Report.

Only samples from participants on active treatment will be analyzed, unless there is a need to confirm the correct treatment has been given to study participants.

Incurred sample reproducibility analysis or additional assay development work, if any, will be performed alongside the bioanalysis of the test samples. The results from the evaluation, if performed, will be reported in a separate Bioanalytical Report.

## 8.5 Pharmacodynamics

### 8.5.1 Collection of Samples for Pharmacodynamics

Samples will be collected, labeled, stored, and shipped as detailed in the Laboratory Manual.

Blood samples will be collected for measurement of LDL-C, lipid profile, ApoA1, ApoB, Lp(a), hsCRP, and PK profile at the time points specified in the SoA ([Table 1](#)).

For storage, re-use, and destruction of samples for PD see [Appendix C](#).

## **8.6        Optional Genomics Initiative**

Collection of optional samples for Genomics Initiative research is also part of this study as specified in the SoA and is subject to participant agreement in the optional genetic research information ICF.

The blood sample for genetic research will be obtained at Visit 2, subject to participant agreement in the optional genetic research information ICF.

Blood samples for DNA isolation will be collected from participants who have consented to participate in the genomic analysis component of the study. Participation is optional.

Participants who do not wish to participate in genomic research may still participate in the study.

See [Appendix D](#) for information regarding the Genomics Initiative genetic samples. Details on processes for collection and shipment and destruction of these samples can be found either in [Appendix D](#) of this protocol or in the Laboratory Manual.

## **8.7        Biomarkers**

### **8.7.1      Mandatory Biomarker Sample Collection**

By consenting to participate in the study the participant consents to the mandatory research components of the study.

- Samples for biomarker research are required and will be collected from all participants in this study as specified in the SoA ([Section 1.2](#)).
- Samples will be tested for safety, PK/PD, and for exploratory research to evaluate their association with the observed clinical responses to AZD0780.

### **8.7.2      Other Study-related Biomarker Research**

Already collected samples may be analyzed on different biomarkers thought to play a role in dyslipidemia, lipid metabolism, metabolic disorders, and/or ASCVD including, but not limited to, blood (plasma and serum) and urine sample analysis to evaluate their association with observed clinical responses to study intervention. Targeted and unbiased metabolomic, lipidomic, and/or proteomic approaches may be used for PD biomarkers and biomarker research relevant to safety, tolerability, PK profile, and efficacy related to AZD0780 treatment.

For storage, re-use, and destruction of biomarker samples see [Appendix C](#).

## **8.8 Immunogenicity Assessments**

Immunogenicity samples are not collected in this study.

## **8.9 Medical Resource Utilization and Health Economics**

Medical resource utilization and health economics parameters are not evaluated in this study.

## **8.10 Study Participant Feedback Questionnaire**

A study participant feedback questionnaire is not included in this study.

# **9 STATISTICAL CONSIDERATIONS**

The SAP will be finalized prior to database lock and it will include a more technical and detailed description of the planned statistical analyses. This section is a summary of the planned statistical analyses of the most important endpoints including primary and key secondary endpoints.

## **9.1 Statistical Hypotheses**

The primary objective is to demonstrate superiority of AZD0780 compared to placebo on LDL-C. To support the primary objective, the primary endpoint is percent change from baseline of LDL-C at Week 12. To strongly control the familywise error rate at the 0.05 level (2-sided), the alpha expenditure will be allocated to test the following null hypotheses (H) for the primary endpoint:

- H1:  $\mu_{AZD0780\text{[REDACTED] mg}} = \mu_{\text{placebo}}$
- H2:  $\mu_{AZD0780\text{[REDACTED] mg}} = \mu_{\text{placebo}}$
- H3:  $\mu_{AZD0780\text{[REDACTED] mg}} = \mu_{\text{placebo}}$
- H4:  $\mu_{AZD0780\text{[REDACTED] mg}} = \mu_{\text{placebo}}$

Where  $\mu$  denotes the percent change from baseline of LDL-C at Week 12.

A hierarchical testing strategy (closed testing procedure) will be employed. H1 will be tested first using the full test mass alpha. If H1 is rejected, then the full test mass will be recycled to test H2. If H2 is rejected, then H3 will be tested with full alpha, and if H3 is rejected, H4 will be further tested with full alpha. Further details of multiplicity testing are provided in the statistical analysis plan (SAP).

## **9.2 Sample Size Determination**

The study will randomize approximately 375 participants in order to have approximately 320 evaluable participants who complete the 12-week treatment period to support the evaluation of the primary endpoint (the discontinuation rate is assumed to be approximately 15%).

Participants will be randomized in a 1:1:1:1:1 manner to receive AZD0780 [ ] mg, [ ] mg, [ ] mg, [ ] mg, or corresponding placebo.

The sample size is driven by the objective to assess the safety and tolerability of AZD0780. The chosen sample size is believed to be sufficient for the creation of a robust safety database.

The sample size of approximately 64 evaluable participants who complete the 12-week treatment period in each arm will provide more than 90% power for the test of each dose of AZD0780 versus placebo to detect a difference of [ ] in percent change from baseline in LDL-C to Week 12. The calculations assume SD = [ ] and a 2-sided alpha level of 0.05, and are based on a t-test with normal approximation for percent change from baseline.

### 9.3 Populations for Analyses

The following populations are defined:

**Table 7 Populations for Analysis**

Population/analysis set	Description
Enrolled	All participants who sign the ICF.
Randomly Assigned to Study Treatment Set	All participants who were randomized. Participants will be analyzed according to the treatment to which they were randomized.
Full Analysis Set	All randomized participants who received at least one dose of study intervention. Participants will be included in the analysis according to the treatment to which they were randomized.
Safety Analysis Set	All randomized participants who received at least one dose of study intervention. Participants will be included in the analysis according to the treatment they actually received.
PK Analysis Set	All participants who received at least one dose of AZD0780 and who had evaluable PK data. Participants will be included in the analysis according to the treatment they actually received.

ICF = informed consent form; PK = pharmacokinetic(s).

## **9.4 Statistical Analyses**

### **9.4.1 General Considerations**

Separate randomization lists will be generated for Japan and for the rest of the world. No stratification factor will be used for statistical analysis.

Statistical tests will be performed using 2-sided tests at the 5% significance level, if not explicitly specified otherwise.

The baseline value is defined as the last non-missing value prior to the administration of the first dose of study intervention unless otherwise stated.

Participant disposition will be summarized and will include the following information (also including the percentage for each category): number of participants randomized, number of participants who received treatment, number of participants who did not receive any treatment, number of participants who completed treatment, number of participants completing the study and the number of participants who were withdrawn (including reasons for withdrawal). Participants and/or data excluded from the analysis set will be listed including the reason for exclusion.

Demographic variables (age, gender, race, ethnicity, height, weight and BMI) will be listed by participant. Demographic characteristics (age, gender, race and ethnicity) and participant characteristics (height, weight, and BMI) will be summarized by treatment (dose level of AZD0780 and placebo) for all randomized participants.

A more comprehensive description of statistical procedures and assessments will be available in the SAP.

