## **6.3 Assignment to Study Intervention**

All participants will be centrally assigned to randomized study intervention using an IRT/RTSM. The participant numbers will be obtained during screening for all participants, after the signature of the ICF, while the randomization codes will be assigned only to the participants proceeding to the treatment phase of the study. Before the study is initiated, the telephone number and call-in directions for the IRT and/or the log in information and directions for the RTSM will be provided to each site in the IRT/RTSM user manual.

In case of rescreening, the rescreened participants should be assigned the same participant number as for the initial screening.

Participants will be randomized to once daily dosing of placebo or different dose levels of AZD0780. Dosing should be supervised and documented by study staff when study intervention is administered in the clinic. Eligible participants will be randomized across 5 different treatment arms (approximately 75 participants in each arm) in a 1:1:1:1:1 ratio for a

12-week treatment period. The planned treatments arms are AZD0780 [redacted] mg, AZD0780 [redacted] mg, AZD0780 [redacted] mg, AZD0780 [redacted] mg, and placebo. A minimum of 5 participants and a maximum of 10 participants in each arm (a minimum of 25 in total and a maximum of 50 in total) will be allocated to sites in Japan. Separate randomization lists will be generated for Japan and for the rest of the world.

Investigational medicinal product will be available as film-coated oral tablets in labeled bottles containing either AZD0780 tablets or placebo tablets (35 tablets in a bottle).

Returned study intervention should not be re-dispensed to participants.

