2 CHANGES TO PROTOCOL PLANNED ANALYSES

- ECG parameters will be presented descriptively, treatment emergent abnormalities will be summarized, shift tables will be produced and key subject information will be listed.
- Multiplicity adjustments will not be applied for any of the secondary endpoints, and will have nominal p-values presented only.
- Two subcategories of the intercurrent event ‘change in background therapy’ are introduced:
 - ‘Change in background lipid lowering statin therapy’
 - ‘Initiation, change or discontinuation in non-prohibited background lipid lowering non-statin therapy’ to account for non-statin therapies (such as ezetimibe and bempedoic acid) when assessing the treatment effects.
- The ICE ‘Prohibited medication intake’ is clarified as ‘intake of prohibited medication affecting lipid parameters’.
- Addition of the ICE ‘Prohibited medication not affecting lipid parameters’, ‘intake of any other concomitant medication’, and ‘death’.

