3.2 Analysis Sets

A minimum of 5 participants and a maximum of 10 participants in each arm (a minimum of 25 in total and a maximum of 50 in total) will be allocated to sites in Japan. Separate randomization lists will be generated for Japan and for the rest of the world to support exploratory investigation of subgroups, if required outside of CSR and to ensure compliance with the Japanese regulations.

Analysis sets are groups of participants who contributed data points to this clinical trial. Analysis sets are defined in [Table 1](#).

If a participant received study intervention from the wrong kit for only a part of the treatment duration and then switched to another, the associated actual treatment group for that participant will be

- the AZD0780 group if the participant has received any dose of AZD0780 and placebo,
- the AZD0780 treatment group the participant had the longest exposure to if a participant has received multiple doses of AZD0780.

Table 1 – Definition of Analysis Sets

Population/analysis set	Description
Enrolled (ENR)	All participants who sign the ICF.
Randomly Assigned to Study Treatment Set (RAND)	All participants who were randomized. Participants will be analyzed according to the treatment to which they were randomized.
Full Analysis Set (FAS)	All randomized participants who received at least one dose of study intervention. Participants will be included in the analysis according to the treatment to which they were randomized.
Safety Analysis Set (SAS)	All randomized participants who received at least one dose of study intervention. Participants will be included in the analysis according to the treatment they actually received.

PK Analysis Set (PKS)	All participants who received at least one dose of AZD0780 and who had evaluable PK data. Participants will be included in the analysis according to the treatment they actually received.
-----------------------	--

ICF = informed consent form; PK = pharmacokinetic(s).

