4.2.1.4 Primary Analysis of Primary Endpoint

The summary measure for the primary endpoint will be the difference in least squares mean of percent change from baseline of direct LDL-C at Week 12. The primary endpoint will be analysed using a MMRM on the FAS. Percent change from baseline in direct LDL-C at each post-baseline visit will be used as the dependent variable. The model will include the fixed effects of baseline direct LDL-C, treatment group, visit, and treatment-by-visit interaction, and the random effect (random intercept) of participant. The Restricted Maximum Likelihood estimation approach will be used with a compound symmetry covariance structure for repeated measures.

In case of non-convergence, an ANCOVA model will be run. The model will include the fixed effects of baseline direct LDL-C and treatment group as covariates. In this model, the dependent variable will be the percent change in direct LDL-C from baseline to Week 12.

The results will be summarized by the difference in least squares means, 95% confidence interval, and p-value.

The hierarchical testing strategy will be employed to strongly control the familywise error rate at the 0.05 level (2-sided), as described in Section 3.3.3.

The primary endpoint will also be characterized by descriptive statistics (as defined in Section 3.3.1) at each scheduled visit and visualized with line plot.

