4.2.1.7 Subgroup Analyses

The primary endpoint will also be assessed based on the intensity of the statin background therapy at baseline. Both descriptive and inferential statistics will be presented.

Additionally, the subgroup analysis will be conducted based on Ezetimibe use at baseline (categorized as ‘Yes’ and ‘No’) and direct LDL-C levels at baseline (categorized as <2.6 mmol/L, >=2.6 mmol/L to <=3.9 mmol/L, and >3.9 mmol/L).

The statistical model described in Section 4.2.1.4 will be applied to each subgroup separately.

If the number of participants is too small within a subgroup, the subgroup categories may be redefined prior to unblinding of the study.

4.2.2 Secondary Endpoint: Percent change from baseline of LDL-C at Week 12

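### Randomisation is stratified by Japan versus rest of world, but the primary MMRM and fallback ANCOVA leave the stratum out: a small, nearly free gain in precision is forgone

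*Protocol*

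**What the plan says.** Protocol 9.4.1 states both halves of the point together: "Separate randomization lists will be generated for Japan and for the rest of the world. No stratification factor will be used for statistical analysis". Protocol 6.3 sets the allocation at 1:1:1:1:1 and fixes the Japanese contribution: "A minimum of 5 participants and a maximum of 10 participants in each arm", that is 25 to 50 of about 375 in total. SAP 3.2 repeats the separate lists and explains that they exist "to support exploratory investigation of subgroups, if required outside of CSR and to ensure compliance with the Japanese regulations".

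The models follow Protocol 9.4.1. For the primary MMRM, SAP 4.2.1.4 says: "The model will include the fixed effects of baseline direct LDL-C, treatment group, visit, and treatment-by-visit interaction", plus a random participant intercept. For the fallback ANCOVA it says: "The model will include the fixed effects of baseline direct LDL-C and treatment group as covariates". Neither contains region. Neither document states a block size for either list.

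**The concern.** When arms are balanced within each list, differences between regions cancel out of the treatment contrast. A model without region still counts those differences as residual noise. Its standard error then exceeds the true sampling variability, confidence intervals are too wide and the test runs below its nominal 5%.

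Two conditions are both needed: region must predict percent change in LDL-C beyond what baseline LDL-C explains, and arms must be near-balanced within each list. On the first, the documents quantify nothing. Protocol Appendix F gives Japan its own list of background statins, with regimens absent from the list for other countries (rosuvastatin 2.5 mg, for example), so a regional gap is plausible but not shown. On the second, the allocation ratio and the range of 5 to 10 per arm make near-balance in Japan likely, but without a stated block size it is not guaranteed.

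What is at stake is a little precision in the primary comparison. SAP 3.2 says why the lists exist; it does not say why the model should ignore them.

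**Working it through.** **The plan's own figures.** Protocol 9.2: 375 × 0.85 = 318.75, stated as about 320 evaluable; 320 / 5 = 64 per arm. These reproduce. The power claim, "will provide more than 90% power for the test of each dose of AZD0780 versus placebo", cannot be reproduced because the difference and SD are redacted. With 64 per arm and two-sided alpha 0.05 it needs a standardised difference above √(2/64) × (1.960 + 1.282) = 0.573.

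**Inputs.** Japanese share per arm p = 5/75 = 6.7% to 10/75 = 13.3% (Protocol 6.3), so p(1−p) = 0.0622 to 0.1156. The regional gap g is in residual SDs after baseline adjustment, assumed equal in all arms. It is an assumption, taken from 0 to 1. Working in SD units avoids the redacted SD.

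**Formulas, lists balanced by arm.**
- SE ratio, region omitted over included: f = √(1 + p(1−p)g²)
- True two-sided size: 2(1 − Φ(1.96 f))
- Power lost from power P: P − Φ(1.96 + z_P − 1.96 f)

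For example, with 10 Japanese per arm and g = 0.5: f = √(1 + 0.1156 × 0.25) = 1.0143.

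| g | SE inflation (5 / 10 per arm) | True size | Points lost at 90% power | At 95% | At 99% |
|---|---|---|---|---|---|
| 0 | none | 0.050 | 0 | 0 | 0 |
| 0.25 | 0.19% / 0.36% | 0.0496 / 0.0492 | 0.07 / 0.12 | – | – |
| 0.5 | 0.77% / 1.43% | 0.0483 / 0.0468 | 0.27 / 0.50 | 0.16 / 0.30 | 0.04 / 0.08 |
| 1 | 3.06% / 5.62% | 0.0434 / 0.0384 | 1.09 / 2.07 | 0.65 / 1.24 | 0.17 / 0.33 |

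**Simulated ANCOVA** (375 participants, exact balance within lists, 20,000 runs, 50 Japanese, g = 1). Region omitted: mean model SE 0.1727 against a true SD of 0.1628, size 0.037. Region included: SE 0.1634, size 0.050.

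**Simulated MMRM** (five visits, compound symmetry by REML, assumed within-participant correlation 0.6, 15% dropout unrelated to outcome, blocks of 5, 4,000 runs, simulation SE of size 0.0034), 25 / 50 Japanese:
- g = 0.5, constant over visits: SE 0.1724 against 0.1711 / 0.1735 against 0.1712; size without region 0.049 / 0.045.
- g = 1, constant: SE 0.1760 against 0.1711 / 0.1800 against 0.1711; size 0.043 / 0.039 without region, 0.050 / 0.049 with it.
- Gap rising linearly from 0 at the first visit to 1 SD at Week 12: SE 0.1729 against 0.1719 / 0.1745 against 0.1725, only 0.6% / 1.2% larger; size 0.049 / 0.047.
- g = 0: size 0.051 with and without region.

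**Dependence on blocking** (Week 12 ANCOVA, g = 1, 8,000 runs, simulation SE 0.0024). Size without region for 25 / 50 Japanese: blocks of 5, 0.045 / 0.037; blocks of 10, 0.043 / 0.039; unblocked, 0.052 / 0.046. The unblocked runs did not enforce the limit of 5 to 10 per arm. With region, size was 0.046 to 0.051 throughout.

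**If arms are not balanced within region.** With region ignored in the allocation (50 Japanese, g = 1), the unadjusted model's SE is correct (0.1726 against a true SD of 0.1731, size 0.051), but the adjusted estimate is more precise (true SD 0.1642). The extreme permitted split of 10 against 5 Japanese shifts the unadjusted contrast by (5/75)g = 0.067g SD. At g = 0.5 that is 0.033 / √(2/75) = 0.2 SE, a chance shift that adjustment would remove.

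**The case against.** The strongest case against is that nothing is broken. The choice is pre-specified, stated openly and followed consistently, and Amendment 2 revisited Protocol 6.3 and 9.4.1. SAP 3.2 gives regulatory and exploratory reasons for the lists and does not claim that region is prognostic. All of that stands, and is why this is not called an error.

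The size can also be challenged. LDL-C and triglyceride entry limits are the same everywhere, Appendix F expects the Japanese statins to lower LDL-C by at least 30%, background therapy is to stay stable, and the endpoint is a baseline-adjusted percent change. A 1 SD gap has no support in the documents. At 0.5 SD the simulated MMRM sizes of 0.049 and 0.045 cannot be told from 0.05. If the gap were a difference in drug response, present only in the four active arms, a main-effect term would recover less: with k = p(1−p)g², the SE ratio is √[(1 + 0.8k)/(1 + 0.16k)], giving 0.5% to 0.9% at 0.5 SD and 2.0% to 3.6% at 1 SD. Protocol 9.2 also says the sample size is driven by safety, so power is not the binding constraint. These points make a small effect smaller; they do not remove it.

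Finally, the change brings exemptions and leaves the imputation and analysis models different by one term. A simplified check (50 Japanese, 15% missing at Week 12, by-arm imputation from baseline and one earlier visit, 20 imputations, 2,500 runs, simulation SE 0.0044) gave size 0.056 and 0.048 at g = 0.5 and 1 without region in the imputation, against 0.054 and 0.047 with it. That shows no detectable harm, but it does not reproduce Appendix A, which uses 1000 imputations and sequential predictive mean matching by treatment and on-treatment status. The reassurance is partial.

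**Conclusion.** The point holds as an optional improvement of low severity. The trial randomises within region and analyses as if it did not. Under balance within lists and a regional gap of up to 0.5 residual SD, the cost is a standard error at most 1.4% too large and at most 0.5 point of power at 90%. At 1 SD it is at most 5.6% and about 2 points. The cost is nil if the gap is zero, and smaller if the gap builds up over visits, is confined to active arms, or true power is well above 90%. If the lists are unblocked, the test size is near nominal and only the gain in precision remains. The primary test is valid as written. Confidence is moderate, because the regional gap and the blocking are both undocumented.

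**What to change.** Add randomisation stratum (Japan / rest of world) as a fixed effect to the MMRM and the fallback ANCOVA in SAP 4.2.1.4, and carry it into the overall analyses of 4.2.2 to 4.2.4. Record the departure from Protocol 9.4.1 before unblinding in SAP Section 2, which already lists comparable changes, such as "Multiplicity adjustments will not be applied for any of the secondary endpoints, and will have nominal p-values presented only".

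Fix the exemptions in the same text, not by looking at sparsity later:
- Leave the term out of all subgroup fits in 4.2.1.7 and 4.2.3.7 and their repeats in 4.2.2.7 and 4.2.4.7. This needs saying because SAP 4.2.1.7 currently provides: "The statistical model described in Section 4.2.1.4 will be applied to each subgroup separately".
- Keep the Appendix A imputation models without region, including the retrieved-dropout step, and state that imputation and analysis models then differ by this one term. At 15% discontinuation, 5 to 10 Japanese per arm gives 0.75 to 1.5 expected discontinuers per arm. The chance that at least one of five arms has none is 1 − (1 − 0.85⁵)⁵ = 95% with 5 per arm and 1 − (1 − 0.85¹⁰)⁵ = 67% with 10.

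The cost is one model term (one degree of freedom out of about 369 in the ANCOVA if all 375 contribute), one bullet in SAP Section 2 and a short statement of the exemptions. No new data and no change to trial conduct are needed.
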